262 wearing the blinded study CGM concurrently during the study period.
- 263 11. Will be reachable by phone and/or email to comply with study procedures.
- 264 12. Will be able to comply with study procedures, per investigator's opinion.
- 265 13. Patient agrees to not use correctional insulin unless BG ≥250 for the 48 hours
266 before and after 1st dose of IDeg.

267

268 **3.6 Exclusion Criteria**

269 Patient must not have ANY of the exclusion criteria to be included in the study.

- 270 1. Patients with eGFR <30 on at least 2 measurements within 1-year of the screening
271 visit.
- 272 2. History of myocardial infarction within 6 months preceding the screening visit.
- 273 3. Patients taking non-insulin medications for the glycemic management of T1D
274 (including metformin, DPP-4 inhibitors, GLP-1 receptor agonists, SGLT-2
275 inhibitors, thiazolidinediones, alpha-glucosidase inhibitors, pramlintide)
- 276 4. Known or suspected allergy to IDeg or one of its excipients.
- 277 5. Pregnant, planning to become pregnant in the next 3 months or breastfeeding.
- 278 6. Participation in a clinical trial with investigational drug within 1 month of the
279 screening visit or at present.

7. Skin condition that prevents the insertion of the CGM.
8. Previously randomized and received drug in this study.
9. Presence of decompensated or poorly controlled psychiatric conditions.
10. Current known or suspected illicit substance use.
11. Any anticipated surgery or procedure in the next 14 days.
12. Patients using U-300 glargine as their basal insulin.
13. Patients using insulin afreZZa as their short-acting insulin.
14. Use of glucocorticoid burst/pulse therapy within 14 days prior to screening visit (chronic stable glucocorticoid doses are acceptable).

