3.7 Withdrawal Criteria

Patients have the right to withdraw from the study at any stage and for any reason.

Patients **may be** discontinued prematurely, by the investigator for any of the following reasons:

- Emergence of a severe condition(s) such that, in the judgement of the investigator, continuation in the trial would negatively impact the health of the patient.
- Lack of compliance with study medication or visits as judged by the Investigator.
- Patient lost to follow-up.
- Major protocol violation.
- Inter-current illness that, in the judgment of the investigator, should result in premature discontinuation.
- Use of prohibited medications (see the Inclusion/Exclusion criteria)
- Onset of glucocorticoid burst/pulse therapy during the study period.
- Knowledge of new risks necessitating new benefit/risk evaluation.
- Patient voices intention to become pregnant in the immediate future.

Patients **must** be discontinued for any of the following reasons:

- If Novo Nordisk determines that the study must be stopped, all patients will be required to end participation at that time.
- Trial closed-out.
- Patient becomes pregnant.

A patient will not be discontinued early from the study solely because of missing the scheduled transition from insulin glargine to IDeg. The research staff will discuss the matter with the patient and determine whether they feel he/she can continue moving forward in the study following all study procedures, including dosing. If after this discussion, the patient and the research team are in agreement about continuing in the study, the investigator will decide if he/she may remain in the study.

A subject cannot be considered lost to follow-up until the research center performs and documents at least three (3) attempts to contact him by phone, email or letter.

323 **3.8 Patient Replacement**

324 Patients discontinuing from the study will not be replaced. IDS will continue to assign
325 randomization of the next participant to a specific group, based on the original
326 randomization plan, when the next participant has completed screening procedures and is
327 ready for randomization. We will include data from all randomized participants in our
328 data analysis.

329

330 **3.9 Rationale for Study Population**

331 The main objective of our study is to determine if the use of a bridging dose of insulin
332 glargine is able to improve glucose control in first few days after the first dose of IDeg.

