505 CGM, per study protocol, while remaining on their original insulin regimen, and to again
506 upload CGM data on day 5. Research staff will review this data on day 5.
507 If there is \geq 38 hours of usable CGM data from day 3-5, they will be instructed to proceed
508 with their first dose of IDeg that night, as scheduled. Subjects with $<$ 38 hours of usable
509 CGM data will be discontinued from the study.
510

511 3.10.5 Telephone Encounter #3:

512 This will be on day 4, i.e. the day after the first bedtime dose of IDeg (or on day 6 for
513 subjects who needed to repeat baseline CGM data collection). We will inquire about
514 adverse events and any change to concomitant medications. The doses of insulin
515 administered will be obtained and documented. The main purpose of this call is to ensure
516 that the subject implemented the transition from insulin glargine to IDeg, correctly. If it is
517 discovered that the subject forgot to transition, then they will be given repeat instructions
518 to dose on night of day 4. If it is discovered that the subject executed the transition
519 incorrectly, then they will need to undergo a 3-day "wash out period", during which they
520 will resume their original insulin glargine regimen (with alterations as deemed necessary
521 by study physician on day 4), and then they will be instructed to execute the transition
522 again on night of day 7. If a subject performs the transition erroneously a second time,
523 he/she will be discontinued from the study and replaced by a new subject as the study
524 supplies allow. Subjects will be instructed not to alter their dose of IDeg for at least the
525 first 3 doses (i.e. 48 hours after 1st dose).
526

527 3.10.6 CGM Removal and Download Visit (Visit 3):

528 Subjects will come in approximately 8 ± 2 days after their CGM insertion. At this visit,
529 their study CGM will be removed and downloaded. We will inquire about adverse events
530 and any change to concomitant medications. We will collect and review their study
531 logbook. They will also be given instructions on how to transition back to insulin
532 glargine.

533

534 **Once-daily glargine users:** Approximately 24 hours after their last dose of IDeg,
535 subjects will be instructed to administer 50% of their original total daily dose of glargine
536 at bedtime. At 48 hours after their last dose of IDeg, they will return to their original
537 bedtime insulin glargine dose.

538

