606 Compliance will be defined by the following (all 3 need to be met to be considered 607
607 compliant), assessed during the 48 hours prior to and after the first dose of IDeg:
611
612

- 608 • No missed doses of basal insulin
- 609 • No missed doses of nutritional insulin with meals
- 610 • Wearing the study CGM for >19 hours a day

613 4. STATISTICAL CONSIDERATIONS:

614 The primary objective of this pilot study is to calculate the change in percent time that 615 BG is “in range” (TIR defined as 70-180 mg/dL) in the 48 hours before the first IDeg 616 dose vs. the 48 hours after the first dose, and to compare the mean of this change between 617 patients who are randomized to receive bridging glargine and those who are randomized 618 to not receive bridging glargine. Randomization will be stratified by glargine use (once 619 vs. twice daily). For each patient, the TIR in the 48 hours before first IDeg use will be 620 calculated, as will the TIR in the 48 hours after first IDeg use. The difference of these 621 values will then be calculated, and the mean of the differences compared between the 622 randomized arms. Our primary hypothesis will assume that the “bridging effect” is 623 similar between patients who take glargine once daily and twice daily. However, we plan 624 an exploratory look at this assumption as a secondary objective.

625

626 If we assume the true change in TIR (before first dose of IDeg minus after first dose of 627 IDeg) to be 0% for the bridging group and 15% for the non-bridging group, and if we 628 assume a common standard deviation of 15% (meaning the distributions of change in TIR 629 are separated by 1 standard-deviation unit), then 20 patients in each group will provide 630 87% power to observe a statistically significant (at the two-sided level of .05) difference 631 in mean change of TIR.

632

633 As noted above, we’ll assess the magnitude of this difference as a function of once- vs. 634 twice-daily glargine use. With only 40 patients, it’s highly unlikely that a statistically 635 significant interaction will be observed, but if the directions of the difference in mean 636 changes are the same in the once-daily vs. twice-daily groups we shall consider the 637 results to be consistent with each other.

638

639 Secondary endpoints to be assessed in a descriptive manner include the following:

- 640 1. Coefficient of variation of TIR for each treatment within each group

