696 The study will begin recruitment of patients immediately following the approval of 697 University of Washington's IRB. We plan to recruit patients over a 12-month period. 698 Following the completion of patient recruitment and data collection, we plan to perform 699 data analysis and complete the integrated final study report over a 4-month period.

700

701 7.1 Study Schedule

Event	Screening Visit	Observation on Glargine		Treatment with IDeg		Follow-Up
	Up to 2 weeks	Day 0	Day 1	Day 3	Day 4 ^a	Day 7 ± 2 ^a Day 14 ± 2 ^a
Informed consent/HIPPA	x					
History/focused exam	x					
Weight and vital signs	x					
Documentation of insulin doses	x	x	x	x	x	x
Documentation of concurrent medications	x	x	x	x	x	x
Inquiry of adverse events		x	x	x	x	x
Download of data from home glucose meter and/or CGM ^b	x					
Labs	x					
Eligibility	x					
Randomization	x ^c					
Study Drug Dispensation				x		
Placement of study CGM		x				
Daily Insulin logbook and hypoglycemia episode form dispensation		x				
Telephone Encounter			x	x	x	x
Collection of data from study CGM Upload				x		
Study Drug Administration				x	x	x
Study Logbook/Hypoglycemia form Collection						x
Download data from study CGM						x ^d

702 a. Day 4, 7, and 14 may be extended by 2 days if patients do not have ≥ 38 hours of
703 usable study CGM data. See Section 3.11.4.704 b. Download of data from patients' CGM will be performed if patients wear their own
705 CGM prior to participating in the study.

GLIDE Study

706 c. Randomization will be performed at the end of the screening visit after patients
707 complete informed consent and have been deemed eligible to participate in the study.
708 d. Downloaded data include all endpoints listed under Section 3.2.
709

710 **7.2 Study Milestones**

711
712
713
714 **8. STUDY DRUGS AND MATERIALS:**

715 **8.1 Study medication(s) / devices(s)**

716 • Insulin glargine, 100 units per mL injected subcutaneously daily, dosage as
717 determined by the clinician and study protocol. Manufacturer: Sanofi or Lilly
718 • IDeg, 100 units per mL injected subcutaneously daily, dosage as determined by
719 the clinician and study protocol. Manufacturer: Novo Nordisk.
720 • Placebo, 9g/L sodium chloride (normal saline) injected subcutaneously daily,
721 dosage as determined by the clinician and study protocol.
722 • Pen needles for injecting insulins.
723 • Dexcom G6 Mobile CGM System, inserted subcutaneously and worn for 3-10
724 days. Manufacturer: Dexcom, Inc.

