791 We will perform a randomized, placebo-controlled intervention study to minimise bias. 792 Study participants will be randomized in a 1:1 ratio to one of two arms within 2 stratified 793 groups groups (see Section 3.3). After a participant has been randomized, a study drug 794 request will be sent to IDS to dispense the study drug. In keeping with the blinded 795 procedure, the patient and research staff will not be aware of treatment assignment. The 796 study drug request sent to IDS will reflect only the dose of bridging insulin they should 797 receive. IDS will then dispense a prefilled syringe of either insulin glargine or matched 798 placebo to reflect this dose, directly to the research participant on the day it needs to be 799 administered. Participants will then administer the study drug at home according to the 800 instructions provided to them by their clinician investigators and/or research staff 801 according to their randomized assignment and the dosing described under Section 802 3.11.2.1.

803

804 8.6 Breaking of Blinded Codes

805 Breaking of the blinded code will not be applicable, as medical emergencies that may 806 possibly associated with treatment with insulin will be no different between the control 807 and the study groups. However, breaking the blinded code may be done if demanded by 808 the patient. Whenever a code is broken, the person breaking the code must record the 809 time, date and reason, as well as his/her initials in the source documents. All codes must 810 be kept throughout the study period. Accountability of all broken or unbroken codes 811 (hard copy or electronic) will be performed at or after trial closure.

812

813

814 9. CONCOMITANT ILLNESSES AND MEDICATIONS:

815 9.1 Definitions:

816 Concomitant illness: any illness that is present at the start of the trial (*i.e. at the first visit*). 817 Concomitant medication: any medication other than the trial product(s) that is taken 818 during the trial, including the screening and run-in periods.

819 Details of all concomitant illnesses and medication must be recorded at trial entry (*i.e. at 820 the first visit*). Any changes in concomitant medication must be recorded at each visit. If 821 the change influences the subject's eligibility to continue in the trial, Novo Nordisk must 822 be informed.

823 The information collected for each concomitant medication includes, at a minimum, start 824 date, stop date or continuing, and indication.

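### Patients are randomised before the baseline CGM check that can remove them undosed; randomising after the check is a cheap way to protect the 20 per arm behind the stated power

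*Combined protocol and SAP*

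**What the plan says.** **Randomisation.** Section 7.1, footnote c: "Randomization will be performed at the end of the screening visit after patients" have consented and been found eligible. Section 3.10.1 agrees: the investigational pharmacy (IDS) randomises once eligibility is established, and the patient is then called back for visit 2, which falls within 2 weeks of visit 1. The first IDeg dose is on day 3 after CGM insertion.

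**The check.** Under section 3.10.4, staff review the upload on day 3. With at least 38 usable hours, the patient goes to IDS that day for the syringe. With fewer, the baseline is repeated to day 5. For those still short, the rule is: "CGM data will be discontinued from the study".

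**Replacement and analysis.** Section 3.8: "Patients discontinuing from the study will not be replaced. IDS will continue to assign" later participants from the original plan. Section 13 also rules out replacement. The one exception (section 3.10.5) is for a second erroneous transition. Section 3.8 also says that every randomised participant is analysed.

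**Dispensing.** Section 8.5: "IDS will then dispense a prefilled syringe of either insulin glargine or matched" placebo, on the day of use, against a request that shows only the dose.

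**Re-entry.** Exclusion 8 (section 3.6) reads: "Previously randomized and received drug in this study".

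**Power.** Section 4 takes the true change in TIR "to be 0% for the bridging group and 15% for the non-bridging group", with a common SD of 15%, and says that 20 per group give "87% power to observe a statistically significant (at the two-sided level of .05) difference" in mean change.

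**The concern.** The CGM check works as an eligibility requirement, since no one may start IDeg without passing it, but it is applied after allocation. That sits badly with section 3.10, under which randomisation waits until eligibility is confirmed. The interval is long for a trial whose arms differ by one injection: up to 14 + 3 = 17 days from randomisation to first dose, or 14 + 5 = 19 with the repeat.

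A patient removed at the check has used an allocation and left a gap in a block of 4, but has no first IDeg dose. The primary endpoint is defined by the 48 hours on either side of that dose, so it does not exist for this patient. Section 3.8 then asks for an analysis that cannot be done, and no method for such patients is given.

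At stake is the analysed sample size. Section 4 makes no allowance for loss, and the margin between 50 screened and about 40 randomised (section 3.4) is spent before randomisation. Nothing in the documents needs the assignment this early. The stratum is known at screening, and the bridging dose is calculated at visit 2 and is the same number of units in either arm.

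**Working it through.** **Inputs from section 4:** difference 15 percentage points (15 − 0), SD 15, two-sided α 0.05, 20 per arm. **Input not in the documents:** the share of randomised patients lost at the check, assumed here at 5% to 20%.

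**Step 1. Reproduce the stated power.** For a two-sample t-test with n per arm, the noncentrality parameter is λ = δ / (σ√(2/n)), with 2n − 2 degrees of freedom. Power is the probability that a noncentral t variable with parameter λ exceeds the two-sided critical value in absolute size. For n = 20, λ = 15 / (15 × √0.1) = 3.162 with 38 degrees of freedom, and power is 86.9%. This rounds to the plan's 87%. The normal approximation gives 88.5%. The stated figure is correct for 20 analysed per arm.

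**Step 2. Remove patients equally from both arms.** With δ = σ, λ = √(n/2).

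| Analysed per arm | Assumed loss | λ | Power | Change from 86.9% |
|---|---|---|---|---|
| 20 | 0% | 3.162 | 86.9% | – |
| 19 | 5% | 3.082 | 85.1% | −1.8 points |
| 18 | 10% | 3.000 | 83.0% | −3.9 points |
| 17 | 15% | 2.915 | 80.7% | −6.2 points |
| 16 | 20% | 2.828 | 78.1% | −8.8 points |

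**Step 3. Small and unequal losses.** One patient lost in total (20 against 19) gives 86.0%. Two lost from one arm (20 against 18) give 85.0%, almost the same as one from each arm. A few losses therefore cost about 1 to 2 points, and power goes below 80% only when fewer than 17 per arm remain.

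**Step 4. Two ways to recover the number.**
- Keep the timing and inflate the number randomised to 20 / (1 − loss) per arm: 20/0.95 = 21.1, so 22; 20/0.90 = 22.2, so 23; 20/0.85 = 23.5, so 24.
- Move randomisation after the check. Failures then fall outside the randomised set, and 20 randomised per arm keep 86.9% as far as this loss is concerned. The price is more patients starting baseline CGM to reach 40 randomised: 40/0.95 = 42.1, so 43; 40/0.90 = 44.4, so 45; 40/0.85 = 47.1, so 48.

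**The case against.** The best defence is that the harm is small and its rate unknown. A patient must fail twice to be removed, and the day-5 repeat is a real safeguard. The study is a proof-of-concept pilot looking for a signal, and its power rests on an assumed difference and SD, so moving from 87% to 83–85% would hardly change what it can conclude. All of this stands and limits the weight of the point.

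The defence is also right that several stronger readings are not supported:

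- **Bias.** A reader might infer that losing randomised patients distorts the comparison. The loss comes before any study drug and, under sections 3.2 and 8.5, while patients and staff are blinded. It cannot depend on treatment received.
- **An underpowered trial.** Below 80% needs a loss of about 20% at this check, and nothing in the documents suggests that.
- **A hard cap of 40.** Section 3.4 plans approximately 40 patients to start IDeg, which could mean 40 dosed. No passage forbids randomising beyond 40, and none provides for it.
- **Permission to re-randomise.** Exclusion 8 does not bar a randomised but undosed patient, but an exclusion is not a permission, and no re-entry route is described. This is a wording gap.
- **The analysis-set conflict.** Section 12 excludes non-compliant patients and also includes everyone randomised. That contradiction exists whatever the timing.

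The defence does not supply a reason for early assignment. Its remaining point, that same-day randomisation tightens the pharmacy workflow, is fair and is counted as a cost.

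**Conclusion.** The point holds as a design improvement of modest size. The protocol places a protocol-driven discontinuation between randomisation and first dose, without replacement and without an allowance in the sample size. The 87% is arithmetically right, but only if every randomised patient is analysed.

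The size rests on an assumed failure rate: 1, 2 or 3 patients lost per arm cost 1.8, 3.9 or 6.2 points of power. The low end is the more plausible because of the repeat. The effect is on precision and block balance, with no bias expected. That last statement relies on the blinding in sections 3.2 and 8.5. Section 8.2 can be read as saying that staff are told the assignment before they enter the drug order, and should be reconciled with them.

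A reader might also infer that moving randomisation secures 87% power. It does not. Compliance exclusions, transition errors and missing post-dose CGM data all come later.

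**What to change.** 1. Have IDS randomise on day 3 (day 5 if the baseline is repeated), after staff confirm that the CGM check is passed and before the syringe is filled. Leave the strata and the blocks of 4 unchanged.
2. Count the approximately 40 patients in section 3.4 from that point.
3. Align section 3.10.1, section 7.1 footnote c, section 8.2 and section 8.5 with the new timing.
4. As a minor wording change, make exclusion 8 read *previously randomized in this study*.

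**Cost.** This is an amendment of wording, with no change to endpoint, analysis or allocation method. In practice, upload review, randomisation, order, filling, labelling and collection must all fit into one day before the 2100 dose. Same-day collection is already planned, but the documents do not say that the syringe is now prepared that day, so IDS should confirm that it can do this. A few more patients may go through baseline CGM, and they come out of the 50 screened.

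**What it leaves.** It removes losses at the baseline check and other losses before randomisation on the dosing day. Later losses need their own allowance, and the conflict in section 12 over who is analysed needs its own resolution. If the timing is kept instead, section 4 should state an expected loss and inflate the number randomised as shown above.

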473 *their blood glucose is >250, both around meals and otherwise.* While we understand that
474 subjects might be reluctant to allow their blood glucose to run in the 180-250 range
475 without correction, we feel this is a necessary part of our study protocol. The main reason
476 for this is that our primary study end point is time in range (TIR). If the change from
477 insulin glargine to IDeg results in more time in the 180-250 range in patients not
478 receiving the bridging dose of glargine, patients are likely to correct this aggressively
479 with the use of correctional insulin. This would dilute any measurable differences in our
480 primary end point (TIR). It would only potentially show differences in the secondary end
481 points of dose and number of correctional insulin used. However, by telling them to avoid
482 bolusing till glucose rises above 250, we will be able to discern any differences in TIR
483 that might arise from the change of basal insulin, while at the same time, not being unsafe
484 for the patients over a 96 hour period of time.

485

486 3.10.3 Telephone Encounters #1:

487 This will be on day 1 (i.e. the day after the study CGM is inserted). We will ensure that
488 the study CGM is working and the subject does not have any questions or concerns.
489 Study staff will also assist the subject with any troubleshooting, if necessary. Subjects
490 will be instructed to upload their CGM data on day 3, for research staff to review it.
491 Subjects will be instructed not to alter their insulin glargine dose for the following 48
492 hours, till the night of day 3, when they transition to IDeg. We will inquire about any
493 adverse events and change to concomitant medications and document doses of insulin
494 being administered by patient.
495

496 3.10.4 Telephone Encounter #2:

497 Research staff will review patient's CGM data upload on day 3. We will inquire about
498 adverse events, any change to concomitant medications and also document doses of
499 insulin being administered.
500 If there is \geq 38 hours of usable CGM data, then they will be instructed to proceed with
501 their first dose of IDeg that night, as scheduled. In order to obtain the bridging dose of
502 insulin glargine or matched placebo, subjects will be instructed to proceed to IDS at the
503 University of Washington to collect their study drug the same day.
504 If there is $<$ 38 hours of usable CGM data, then subjects will be instructed to wear their

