982 prescribe patients with glucagon kit to be used for treatment of hypoglycemia as needed.
983 Patients will have access to medical providers at the DCC by phone or e-care
984 communication if additional guidance is needed in the event of overdose by the study drug
985 during the study.

986

987

11. LIABILITY AND SUBJECT INSURANCE:

988

989 During and following a subject's participation in the clinical trial, the investigators and
990 their institution will provide adequate medical care to the study subject for any study-
991 related adverse events, including clinically significant laboratory values related to the
992 study. This medical care for study subjects will be provided regardless of their insurance
993 status.

994

995 The investigators will be responsible for the conduct of the study and agree to defend,
996 indemnify, and hold harmless Novo Nordisk, any of its parent companies, affiliates, or
997 subsidiaries, and their respective officers, directors, employees, agents, representatives,
998 distributors, salespersons, customers, licensees, and end-users from and against any claim,
999 suit, demand, loss, damage, expense or liability imposed by any third party arising from or
1000 related to: (a) any breach of Novo Nordisk-investigators' obligations or representations; or
1001 (b) Novo Nordisk-investigators' negligent or grossly negligent use or willful misuse of the
study drug, the results, or services derived therefrom. This

GLIDE Study

1002 indemnification shall not apply in the event and to the extent that a court of competent
1003 jurisdiction or a duly appointed arbiter determines that such losses or liability arose as a
1004 result of Novo Nordisk's gross negligence, intentional misconduct, or material breach of
1005 its responsibilities.

1006

1007

1008 12. EVALUABILITY OF SUBJECTS:

1009 For all analyses, patients not meeting the compliance criteria of the study listed under
1010 Section 3.13 will not be included in the analyses. Clinician investigators will determine
1011 patients' compliance with study drug based on patient's recorded log and patients' time
1012 spent wearing CGM after CGM data has been downloaded at the follow-up visit. We will
1013 include data from all randomized participants in our data analysis. The subjects or
1014 observations to be excluded, and the reasons for their exclusion will be documented and
1015 signed by the clinician investigators or staff prior to database release. The documentation

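### Section 12 drops non-compliant patients from every analysis and two sentences later keeps all randomised patients; Section 4 does not say which set gives the primary time-in-range (TIR) result

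*Combined protocol and SAP*

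**What the plan says.** - **Section 12, first sentence:** "For all analyses, patients not meeting the compliance criteria of the study listed under" Section 3.13 are left out of the analyses.
- **Section 12, third sentence:** the study will "include data from all randomized participants in our data analysis".
- **Section 12, fourth sentence:** exclusions are again assumed, since the subjects or "observations to be excluded, and the reasons for their exclusion will be documented and" signed before database release.
- **Section 3.8:** "We will include data from all randomized participants in our" data analysis. It also says "Patients discontinuing from the study will not be replaced".
- **Section 3.13:** compliance means no missed basal dose, no missed mealtime insulin, and "Wearing the study CGM for >19 hours a day". All three must be met, "assessed during the 48 hours prior to and after the first dose of IDeg".
- **Section 3.10.4:** before the first IDeg dose there is a separate data gate. With at least "38 hours of usable CGM data, then they will be instructed to proceed with" the first dose. A patient who falls short again on the Day 5 upload is discontinued.
- **Section 4:** the mean within-patient change in TIR is compared between randomised arms. No analysis set, sensitivity set or rule for a missing TIR is given.
- **Section 7.1, note c:** randomisation takes place at the end of screening, before any of these conditions can be assessed.

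**The concern.** The plan does not fix which patients produce the primary result. With 20 per arm, a few patients can change the estimate, and an unnamed set can be chosen once results are known.

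The two rules also differ in kind. The all-randomised rule keeps the comparison that randomisation created. The compliance rule removes patients for events after randomisation, and the second half of its window is the period in which post-dose TIR is measured. If glucose during that period leads a patient to skip a mealtime dose, the patient leaves the analysis for a reason tied to outcome and possibly to arm.

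Section 3.13 also mixes behaviour (missed doses) with data sufficiency (CGM wear). A missed dose does not prevent TIR from being calculated; too little CGM data can.

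**Working it through.** **1. Can both rules hold?** Only if no randomised patient fails any Section 3.13 criterion. One failure puts the same patient out under the first sentence and in under the third. The third sentence cannot be met literally either: a patient discontinued under 3.10.4 is already randomised and has no post-dose TIR.

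**2. The plan's power figure.** Inputs from Section 4: difference 15, SD 15, 20 per arm, two-sided 0.05. For a two-sample t-test (noncentral t), the noncentrality is difference / (SD × √(2/n)) = 15 / (15 × √0.1) = 3.162 with 38 degrees of freedom. Power is 86.9%, which reproduces the stated 87%.

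**3. Power under each rule.** The documents give no non-compliance rate, so the rates below are assumptions, equal in both arms.
- Excluded, unrelated to outcome: n = 20 × (1 − f) per arm, difference still 15.
- Kept: n = 20 per arm, difference 15 × [(1 − f) + f × k], where k is the share of the effect that non-compliers retain. SD is held at 15.

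| Assumed f | Excluded: n per arm, power | Kept, k = 0: difference, power | Kept, k = 0.5: difference, power |
|---|---|---|---|
| 10% | 18, 83.0% | 13.5, 79.2% | 14.25, 83.3% |
| 20% | 16, 78.1% | 12.0, 69.3% | 13.5, 79.2% |
| 30% | 14, 72.1% | 10.5, 57.8% | 12.75, 74.5% |

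Holding SD at 15 flatters the kept set. Suppose direct-conversion non-compliers sit at the bridging mean. At f = 20% the variance in that arm is 225 + 15² × 0.2 × 0.8 = 261. Averaged with 225 this is 243, so SD is 15.59 and power about 66% instead of 69.3%. At 30% the variance is 272.25, the average 248.6, SD 15.77 and power about 54% instead of 57.8%. The two sets break even when non-compliers retain about 42% to 46% of the effect with SD at 15, or about 46% to 51% with the wider spread.

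**4. How large could bias be?** Assumptions: no true difference, SD 15, 20 per arm, exclusion driven by a latent variable with correlation 0.5 to the outcome, 200,000 simulated trials. The 0.5 and the splits are illustrative.

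| Excluded (arm 1, arm 2) | Shift in difference, points | False-positive rate |
|---|---|---|
| 2, 0 | 1.4 | 6.2% |
| 3, 1 | 1.2 | 6.2% |
| 4, 0 | 2.5 | 8.1% |
| 2, 2 | 0 | 5.5% |
| 4, 4 | 0 | 5.8% |

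At correlation 0 there is no shift and the rate is about 5%. For scale, the planned difference is 15 points.

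**5. Are the two CGM rules one rule?** 2 × 19 = 38, but they differ. Section 3.13 concerns hours worn, strictly above 19 on each day. Section 3.10.4 concerns usable hours in total, at least 38, before the dose. A patient with 24 + 14 hours reaches 38 but fails 3.13, and so does one with exactly 19 + 19.

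**6. Repeated transitions.** Section 3.10.5 has an incorrect transition repeated on Day 7 after a return to glargine, while the endpoint is tied to the first IDeg dose. The 48 hours after a failed first attempt can include that return. The 48 hours before the repeat may include residual IDeg. With the 25-hour half-life in Section 1, simple exponential decay and one dose on Day 3, 0.5^(48/25) = 26% remains at the start of that window and 0.5^(96/25) = 7% at its end.

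**The case against.** The strongest reply is that this is a blinded pilot looking for a signal, with descriptive secondary endpoints. Exclusions are signed before database release, and failures before the first dose cannot be caused by the blinded syringe. This largely stands as an answer on bias. A reader might infer that the first sentence of Section 12 will distort the result. The documents do not support that: they give no non-compliance rate and no sign that it differs by arm, and equal exclusions produce no shift in step 4. The safeguards do not say which set is primary, however, and compliance is judged after the download of the CGM data that hold the outcome.

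A second reply is that Section 4's reference to randomised arms already settles the matter. It leans towards an as-randomised comparison, but it does not override a sentence that covers all analyses.

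A third is that keeping everyone costs power. That can be true, and the cost is larger than a fixed SD suggests (step 3). A reader might conversely infer that keeping everyone protects power; the figures do not support that either.

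On replacement, the plain conflict is between 3.10.5, which replaces a patient after a second transition error, and 3.8. Section 13 speaks of patients who stop study drug or withdraw consent, so it needs checking but is not clearly contradicted. Replacement decides who is recruited, not who is analysed, and is a smaller matter.

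**Conclusion.** The point holds and must be fixed. Section 12 gives two incompatible analysis sets, Section 3.8 repeats one of them, and nothing in Section 4 or elsewhere decides between them. The first sentence is wrong as written, because it makes a post-randomisation exclusion, with a window overlapping the outcome window, apply to every analysis.

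Any bias is possible but of unknown size and direction. The 1.2 to 2.5 point shifts rest on an assumed correlation and unequal exclusions. The 87% power figure is correct for 20 analysed per arm with the full difference, but makes no allowance for non-compliance. At an assumed 20% it becomes 78.1% with exclusion, or about 66% to 69% with inclusion and no arm difference among non-compliers. The reason to prefer all randomised patients is protection of the randomised comparison, not power.

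**What to change.** 1. Delete the first sentence of Section 12. State in Sections 4 and 12 that the primary TIR comparison includes all randomised participants with a computable TIR, by assigned arm, regardless of missed basal or mealtime doses.
2. Make the set meeting all of Section 3.13 a labelled sensitivity analysis.
3. State, before database release, one CGM data minimum for a computable TIR in both windows. The 38 usable hours in 3.10.4 are a natural candidate, but applying them after the dose is a new rule and should be presented as one.
4. The minimum is itself a post-randomisation condition. Report by arm, with reasons, everyone randomised without a computable TIR, and limit Section 12's sentence on exclusions to those cases.
5. Apply the all-randomised principle to the secondary endpoints, including correction boluses. Do not apply the compliance exclusion to adverse event summaries.
6. Smaller linked points: reconcile replacement in 3.10.5 with 3.8 and check it against Section 13. State before database release which 48-hour windows count for a patient who repeats the transition, given the problems with both windows in step 6.

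Cost: wording in Sections 3.8, 3.10.5, 3.13, 4 and 12 (and 13 if needed), one sensitivity analysis and one by-arm table. The downside is possible dilution of the effect by non-adherent patients, as sized above.
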